1.3 Schedule of Activities

Table 1-1: Schedule of Activities

Visit ^a / Week	Screening	Initial Treatment Period (weeks after first dose)							Maintenance Treatment Period (weeks after first dose)				SFU ^b
		Baseline (first dose)	1	2	4	8	12	16	20	24	28	32/ PEOT	
Protocol activity													
Informed consent	X												
Inclusion/exclusion	X	X											
Urine drug screen	X												
Demographic data	X												
Psoriasis history	X												
Significant past medical history and concomitant diseases	X	X ^{c,d}											
DLQI		X			X			X	X	X		X	
PSD (P-SIM)													
Physical exam ^e	X	X						X				X	X
Height		X											
Body weight	X	X										X	
Vital signs ^f	X	X			X			X	X			X	X
Hematology and biochemistry	X	X			X			X	X	X		X	X

Table 1-1: Schedule of Activities

Protocol activity	Visit ^a / Week	Screening	Initial Treatment Period (weeks after first dose)						Maintenance Treatment Period (weeks after first dose)				SFU ^b	
			Baseline (first dose)	1	2	4	8	12	16	20	24	28		32/ PEOT
Urinalysis		X	X						X				X	X
ECG		X												
Pregnancy testing ^g		X	X	X	X	X	X	X	X	X	X	X	X	X
Hepatitis B and C testing ^h		X												
HIV testing ⁱ		X												
Chest x-ray/CT scan ^j		X												
IGRA TB test		X										X		
TB questionnaire		X	X						X			X	X	
Blood sample for BKZ plasma concentration			X	X			X		X		X		X	
Blood sample for anti-BKZ antibodies			X				X		X		X		X	X
PASI		X	X	X	X	X	X	X	X	X	X	X	X	
IGA		X	X	X	X	X	X	X	X	X	X	X	X	
Percentage of BSA		X	X	X	X	X	X	X	X	X	X	X	X	
Scalp IGA ^k			X	X	X	X	X	X	X				X	
Concomitant medication		X	X	X	X	X	X	X	X	X	X	X	X	X

Table 1-1: Schedule of Activities

Protocol activity	Visit ^a / Week	Screening	Initial Treatment Period (weeks after first dose)						Maintenance Treatment Period (weeks after first dose)				SFU ^b	
			Baseline (first dose)	1	2	4	8	12	16	20	24	28		32/ PEOT
AEs/ADE and device deficiency assessment		X	X	X	X	X	X	X	X	X	X	X	X	X
IRT ^l		X	X	X	X	X	X	X	X	X	X	X	X	X
BKZ or placebo administration ^{m,n}			X			X	X	X	X	X	X	X		

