7 DISCONTINUATION OF IMP AND PARTICIPANT DISCONTINUATION/WITHDRAWAL

7.1 Discontinuation of IMP

A study participant should be withdrawn from IMP and will be asked to come back for the SFU Visit 17 weeks after the final dose of IMP if any of the following events occur:

1. Study participant develops an illness that, in the opinion of the Investigator, would interfere with his/her continued participation if the risk of continuing participation outweighs the potential benefit.

2. Study participant develops erythrodermic, guttate, or pustular form of PSO.
3. Study participant is noncompliant with the study procedures or medications in the opinion of the Investigator.
4. Study participant uses prohibited concomitant medications (as defined in Section 6.5.2) that may present a risk to the safety of the study participant or the integrity of the study data, in the opinion of the Investigator and/or the Medical Monitor.
5. Study participant has a clinical laboratory value meeting any of the following criteria:
 - Hepatotoxicity as described in Section 7.1.1.
 - A laboratory value meeting any of the following criteria:
 - Absolute neutrophil count $<1.0 \times 10^3/\mu\text{L}$
 - Absolute lymphocyte count $<0.5 \times 10^3/\mu\text{L}$

A study participant may remain in the study if the result is transient. A retest is required within 1 to 2 weeks at a scheduled or unscheduled visit. If the repeat absolute neutrophil count or absolute lymphocyte count is still below the allowable values, the study participant must be withdrawn. If the repeat absolute neutrophil count or absolute lymphocyte count is above the allowable values, the study participant may continue in the study.

6. There is confirmation of a pregnancy during the study, as evidenced by a positive pregnancy test. See Section 10.4 (Appendix 4) for more information regarding pregnancies.
7. Study participant experiences a severe AE, an SAE, or a clinically significant change in a laboratory value that, in the opinion of the Investigator, merits the discontinuation of IMP and appropriate measures being taken.
8. Study participant considered as having either a suspected new LTBI or who develops an active TB or NTMB infection during the study must be immediately discontinued from IMP, and a PEOT Visit must be scheduled as soon as possible, but not later than the next regular visit.

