3 POPULATIONS FOR ANALYSIS

The Enrolled Set (ES) will consist of all study participants who have given informed consent.

The Randomized Set (RS) will consist of all randomized study participants.

The Safety Set (SS) will consist of all study participants who receive ≥ 1 dose of IMP (bimekizumab or placebo).

The Full Analysis Set (FAS) will consist of all randomized study participants who receive ≥ 1 dose of IMP and have a valid measurement for each of the co-primary efficacy endpoints at Baseline.

The Active Medication Set (AMS) will consist of all study participants who receive ≥ 1 dose of active IMP (bimekizumab).

The Maintenance Set (MS) will consist of all study participants who receive ≥ 1 dose of active IMP (bimekizumab) in the Maintenance Treatment Period.

The Per-Protocol Set (PPS) will consist of all study participants in the RS who have no important protocol deviations affecting the co-primary efficacy endpoints. Important protocol deviations

will be predefined, and study participants with important protocol deviations will be evaluated during ongoing data cleaning meetings prior to database lock. The classification of PPS will be determined at blinded data evaluation meeting before unblinding of the data. The classification of study participants with important protocol deviations related to treatment group information will be re-determined after general unblinding.

The Pharmacokinetics Per-Protocol Set (PK-PPS) will consist of all randomized study participants who receive ≥ 1 dose of active IMP (bimekizumab) and provide ≥ 1 quantifiable plasma concentration post dose without important protocol deviations that would affect the concentration.

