4.1.3 Mapping of assessments performed at Early Discontinuation Visit

If the PEOT visit occurs at a scheduled visit as outlined in the schedule of assessments, then no mapping is necessary, and any PEOT assessments should correspond to that scheduled visit. PEOT visit assessments that occur on a date after a scheduled visit will be assigned to the next scheduled site visit per the protocol following the last visit where assessments were available regardless of the given assessment actually collected per the protocol SoA.

This approach means that there is a chance that data will be mapped to a visit where a given assessment was not actually collected per the protocol SoA. If that happens, those data will not be summarized in by-visit tables (though they will be available in the listings).

The only exception to the above rule is for anti-bimekizumab antibody assessments, in which all PEOT visit assessments will be assigned to the next scheduled visit at which anti-bimekizumab antibody are assessed.

All by-visit summaries will contain nominal visits only. Unscheduled visits will not be mapped to scheduled visits. However, in cases where vendor data (questionnaire data such as PASI, IGA, PSD, scalp IGA, and DLQI data) is assigned to an unscheduled visit instead of a scheduled visit, the assessments will be mapped into the scheduled visit if the assessments dates fall into the permissible window, as detailed in Section 4.1.

Note that based on the early withdrawal mapping conventions described above, a mapped PEOT visit is considered as observed at that visit and should be summarized as such in the tables.

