The following summary will be provided for the Initial and Maintenance Treatment Period (combined) for the AMS by trough plasma concentration tertiles:

- TEAEs and infection TEAEs (TEAEs which code to the SOC of “Infections and infestations”) will be summarized by bimekizumab trough plasma concentration tertiles based on Week 32 PK samples. Study participants with missing Week 32 PK samples will not be included.

The summary will include the number of TEAEs and infection TEAEs, number of study participants with TEAEs and infection TEAEs, percentage of study participants with TEAEs and infection TEAEs, EAIR with 95% CI, and EAER. Infection TEAEs will be sorted by SOC, High Level Group Term (HLGT), HLT and PT. Fungal infections and candida infections will be identified based on MedDRA classification; a separate table does not need to be produced to summarize these events.

In addition, all summaries of TEAEs based on “100 participant years” will include EAIR (with 95% CI) and EAER.

By-study participant listings on all AEs, all serious AEs, and all deaths will be provided on the ES. By-study participant listings based on TEAEs related to study medication and TEAEs leading to study discontinuation will be provided on the SS. A by-study participant listing for device deficiency will also be provided based on the SS.

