4.6.1.4 Immunogenicity

4.6.1.4.1 Definitions

4.6.1.4.1.1 ADAb sample status (positive, negative, missing)

The ADAb sample results will be provided as “Positive Screen” (PS) or “Negative Screen” (NS). For samples presenting ADAb levels that are PS, a further confirmatory assay will be performed, and the result will be reported as either “Positive Immunodepletion” (PI) or “Negative Immunodepletion” (NI).

The ADAb status for each sample will be derived as follows:

- Sample values that are either NS, or PS and NI and where the bimekizumab concentration is less than the validated ADAb assay drug tolerance limit ($200\mu\text{g/mL}$) will be defined as ADAb-negative. Since the bimekizumab concentration is not collected at the SFU visit, the ADAb status will be defined as ADAb-negative if the ADAb sample values are either NS, or PS and NI at the SFU visit.
- Sample values that are either NS, or PS and NI and where the bimekizumab concentration exceeded the validated ADAb assay drug tolerance limit will be defined as inconclusive. Since the bimekizumab concentration is not collected at the SFU visit, the ADAb status will be defined as ADAb-negative if the ADAb sample values are either NS, or PS and NI at the SFU visit.
- Sample values that are PS and PI will be defined as ADAb-positive (regardless of availability of a titer value).
- Missing or non-evaluable samples will be defined as missing.

The PI samples will be titrated and the ADA_b titer (reciprocal dilution factor including minimum required dilution) will be reported. The PI samples will also be analyzed in a neutralizing assay to evaluate the anti-bimekizumab antibody neutralized target binding of bimekizumab (IL-17AA or IL-17FF or both) in vitro.

4.6.1.4.1.2 Cumulative ADA_b status

The ADA_b status (positive, negative, or missing) will be considered in a cumulative manner at each time point.

A study participant will be counted positive from the first visit at which the study participant achieved a positive ADA_b sample result to the end of the treatment period, regardless of any missing/inconclusive or negative ADA_b sample result.

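### The TEAE summary by Week 32 trough tertile is labelled as the AMS but leaves out bimekizumab-treated participants who stop and leave before Week 28, together with their events

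*SAP*

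**What the plan says.** SAP 4.5.2.2 sets the period and analysis set: "The following summary will be provided for the Initial and Maintenance Treatment Period (combined) for the AMS by trough plasma concentration tertiles". The grouping variable is "bimekizumab trough plasma concentration tertiles based on Week 32 PK samples". The exclusion follows at once: "Study participants with missing Week 32 PK samples will not be included". The outcomes are all TEAEs and infection TEAEs, shown as event counts, participant counts and percentages, EAIR with 95% CI, and EAER.

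Membership of the AMS (SAP section 3) needs only one dose of bimekizumab. It does not require reaching Week 32.

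In the protocol's Schedule of Activities, PK samples are taken at Baseline, Weeks 1, 8, 16 and 24, and in the shared Week 32/PEOT column. SAP 4.6.1.4.1 confirms the gap after that: "Since the bimekizumab concentration is not collected at the SFU visit".

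For early leavers, SAP 4.1.3 says: "PEOT visit assessments that occur on a date after a scheduled visit will be assigned to the next scheduled site visit per the protocol". A PEOT visit that coincides with a scheduled visit keeps that visit's label. The only exception to the mapping is for anti-bimekizumab antibodies; PK has none.

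Protocol 7.1 lists reasons to stop IMP and asks those participants back for safety follow-up. The reasons include a severe AE or SAE that the investigator judges to warrant stopping. For suspected new latent TB, active TB or nontuberculous mycobacterial infection, the participant "must be immediately discontinued from IMP, and a PEOT Visit must be scheduled as soon as possible".

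**The concern.** The table classifies events from the first active dose onward by a measurement taken at the end of treatment. A participant must stay long enough to supply that measurement, and some leave because of the very events being counted. Infection is one of the two tabulated outcomes, and certain infections are reasons for stopping IMP. Exclusion can therefore depend on the outcome.

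The SAP gives no fallback concentration, no column for unclassified participants and no note that the table is conditional. A reader who sees AMS in the title would take it as the relation between exposure and TEAEs in everyone given bimekizumab. It actually describes those who stayed to about Week 28 or later. It is also the only TEAE-by-concentration summary that the SAP specifies, so the treatment-group tables cannot show the same relation for the missing participants.

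**Working it through.** The documents give no expected dropout, TEAE rate or tertile size for this table, so there is no planned figure to reproduce. The check has two parts.

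**1. Which PEOT samples become Week 32 samples?** Inputs: the visit list and PK visits (Protocol 1.3), the dosing visits Baseline and Weeks 4, 8, 12, 16, 20, 24 and 28 (SAP 6.11), and the mapping rule (SAP 4.1.3). For a PEOT visit held after the last attended scheduled visit:

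| Last scheduled visit attended | Dosing visits reached | PEOT sample labelled | Week 32 sample? |
|---|---|---|---|
| Baseline | 1 of 8 | Week 1 | No |
| Week 1 | 1 of 8 | Week 2 | No |
| Week 2 | 1 of 8 | Week 4 | No |
| Week 4 | 2 of 8 | Week 8 | No |
| Week 8 | 3 of 8 | Week 12 | No |
| Week 12 | 4 of 8 | Week 16 | No |
| Week 16 | 5 of 8 | Week 20 | No |
| Week 20 | 6 of 8 | Week 24 | No |
| Week 24 | 7 of 8 | Week 28 | No |
| Week 28 | 8 of 8 | Week 32 | Yes |

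Nine of the ten stopping intervals lead to exclusion, including every one with a planned dosing visit still ahead. The only route in is a PEOT after the Week 28 visit, when all eight dosing visits have normally taken place. The safety follow-up visit cannot help, because no concentration is taken there. Missing PK values are not imputed (SAP 4.6.1.1).

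**2. How far could the tabulated incidence move?** Let N be the number in the AMS, E the number with any TEAE, and k the number who stop early because of a TEAE and are dropped. Incidence changes from E/N to (E − k)/(N − k). Assumptions, none of them in the documents: N = 120, true incidence 50% (E = 60) or 75% (E = 90), and k = 2, 6 or 12. N = 120 is the planned total and so an upper limit, because placebo participants who stop before receiving bimekizumab never enter the AMS.

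| k | From 50.0% | From 75.0% |
|---|---|---|
| 2 | 58/118 = 49.2% | 88/118 = 74.6% |
| 6 | 54/114 = 47.4% | 84/114 = 73.7% |
| 12 | 48/108 = 44.4% | 78/108 = 72.2% |

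The effect is larger if the losses fall in one tertile. Take an assumed tertile of 40 with 12 infections (30.0%) and hold its boundaries fixed. Losing 2 affected participants gives 10/38 = 26.3%; losing 4 gives 8/36 = 22.2%. EAIR and EAER change as well, since both events and time at risk are removed.

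**The case against.** The strongest reply is that this is ordinary complete-case handling, openly stated, in one descriptive table with no hypothesis test. The main TEAE, serious TEAE and discontinuation tables on the SS and AMS keep these participants. So do the AE listings and the listing of all PK concentrations for the AMS. Protocol 9.3.1 expects few discontinuations before Week 16. Stopping for a severe AE or SAE is the investigator's judgement, and Protocol 7.1.3 allows IMP to be interrupted for an important infection and restarted. Such a participant may still have a Week 32 sample. All of this stands and limits the reach of the point. It does not make the AMS label correct.

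Three stronger readings are tempting, and the documents do not support them.

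- A reader might infer that the table is biased toward showing no relation and so falsely reassures. That holds only if those who stop for an AE tend to have high exposure. Nothing in the documents shows this, and participants who leave for unrelated reasons are dropped too.
- A reader might note that 90 × 28 + 30 × 12 = 2,880 of the planned 90 × 32 + 30 × 16 = 3,360 bimekizumab person-weeks (86%) precede Week 28, and infer that most relevant events are lost. Under an assumed constant hazard, that fraction applies to TEAEs leading to permanent discontinuation of IMP. This table does not break out that category, and it has its own full AMS table.
- A reader might infer that this is the programme's only exposure-safety analysis. SAP 4.6.1.3 leaves room for model-based PK analyses reported separately, although it does not commit to a safety analysis.

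**Conclusion.** The point holds for this table. Bimekizumab-treated participants who stop IMP and leave before Week 28 are left out with all their events and time at risk, so the table is conditional on remaining to about Week 28 or later and does not describe the AMS as labelled. This follows from the SAP's own rules and needs no assumption about rates. It does not cover every early stopper: a participant whose PEOT follows the Week 28 visit, or who still attends Week 32 and gives a sample, is kept.

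The size does rest on assumptions. With 2 to 6 of 120 stopping because of a TEAE, a 50% any-TEAE incidence becomes 49.2% to 47.4%. The shift is probably small if few stop early, and could be larger within one tertile. The direction of any bias across tertiles cannot be determined in advance. No test and no other safety table is affected. It is a cheap improvement, not a threat to the trial's safety reporting.

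**What to change.** In SAP 4.5.2.2, replace the exclusion sentence with a fourth column headed 'no Week 32 PK sample'. For those AMS participants it should give n, TEAEs, infection TEAEs, time at risk, EAIR with 95% CI, and EAER. Label the three tertile columns as conditional on a Week 32 sample. The four columns then add up to the AMS and no event is lost.

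Replacing the missing value with the last available trough is not a clean alternative. In the bimekizumab arm, the Week 8 and Week 16 pre-dose samples follow 4-week dosing, while the Week 24 and Week 32 samples come 8 weeks after the active doses at Weeks 16 and 24 (Protocol Table 6-2). Those who leave before Week 24 would be ranked on 4-week troughs against completers' 8-week troughs. That could push AE leavers into the top tertile simply because of when they left. If a supportive version with an earlier trough is wanted, it should:

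- compare only troughs from the same visit and dosing interval, for example Week 16 pre-dose in the bimekizumab arm;
- not mix 4-week and 8-week troughs;
- not treat a placebo participant's Week 16 pre-dose sample as on-treatment.

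The cost is a change of SAP wording and one reprogrammed table, with no new data. The downside is an extra column that may hold few participants.

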4.5.2.3 COVID-19 impact on AEs

Not applicable.

4.5.2.4 Other safety topics of interest

The following are AEs of other safety topics of interest that require special statistical analyses and will be provided based on 100 participant years by SOC and PT in two different ways: by treatment in the ITP for the SS, and by treatment in the Initial and Maintenance Treatment Period (combined) for the AMS.

There will be a table which displays the risk difference and the associated 95% CIs for each of the topics of interest in the ITP. A corresponding figure (with dot plots) will be prepared. A summary of each safety topics of interest in the Initial and Maintenance Treatment Period (combined) for the AMS will also be provided.

A by-study participant listing of all AEs of safety topics of interest will be presented by type of safety topics of interest for the SS.

4.5.2.4.1 Infections (serious, opportunistic, fungal and Tuberculosis (TB))

Serious infections will be identified based on MedDRA classification (SOC “Infections and infestations”) using the “Any Serious AE (SAE)” table.

Fungal infections will include all TEAEs (serious and non-serious) which code into the HLTG “Fungal infectious disorders”.

Opportunistic infections (including tuberculosis) will include all opportunistic infection TEAEs identified using UCB-defined search criteria which were adjudicated as opportunistic infections.

4.5.2.4.2 Malignancies

These events will be identified based on the criteria SMQ = “Malignant tumours (SMQ)”.

SMQ search should include all TEAEs which code to a PT included in the Scope=Narrow group within each SMQ.

“Any Malignancy excluding non melanomic skin cancers” will also be summarized based on SMQ=“Malignant tumours (SMQ)”, excluding those AEs which code to an HLT of “skin neoplasms malignant and unspecified (excl melanoma)”.

4.5.2.4.3 Cardiovascular events

For evaluation of potential major adverse cardiac event (MACE), cardiovascular events will include all TEAEs with PT of “Cardiac death” or “Sudden death” and TEAEs which code to a PT included in the Scope=Narrow group within the following SMQs:

- Central nervous system haemorrhages and cerebrovascular conditions (SMQ)
- Ischaemic heart disease (SMQ)
- Embolic and thrombotic events (SMQ)

4.5.2.4.4 Neutropenia

Neutropenia will include TEAEs with the following PTs (regardless of seriousness):

- Autoimmune neutropenia
- Band neutrophil count decreased
- Cyclic neutropenia
- Febrile neutropenia
- Idiopathic neutropenia
- Neutropenia
- Neutropenic infection

- Neutropenic sepsis
- Neutrophil count decreased

4.5.2.4.5 Suicidal Ideation and Behavior (SIB)

SIB events will include all TEAEs which code to a PT included in the Scope=Narrow group within “Suicide/self-injury (SMQ)”. Neuropsychiatric AEs will be identified based on MedDRA SOC psychiatric disorders using the “any TEAE table”.

4.5.2.4.6 Inflammatory bowel disease (IBD)

IBD events will include all TEAEs with HLT “Colitis (excl infective)”.

4.5.2.4.7 Hypersensitivity (including anaphylaxis)

Anaphylactic events will be identified based on the MedDRA anaphylaxis Algorithm (see Section 6.12) for acute anaphylactic events (reported on the same day as when an injection was administered or one day after).

Hypersensitivity events will be identified using the SMQ “Hypersensitivity (SMQ)”. All TEAEs which code to a PT included in the Scope=Narrow search will be included. In addition, serious hypersensitivity events will be identified using the SMQ “Hypersensitivity (SMQ)”. All serious TEAEs which code to a PT included in the Scope=Narrow search will be included.

Furthermore, injection site reactions will be identified using the HLTs: “Administration site reactions NEC” and “Injection site reactions”.

4.5.2.4.8 Hepatic events and drug-induced liver injuries (DILIs)

Hepatic events will be identified based on the SMO of “Drug related hepatic disorders - comprehensive search (SMQ)”. However, these 2 sub-SMQs are to be excluded: “Liver neoplasms, benign (incl cysts and polyps) (SMQ)” and “Liver neoplasms, malignant and unspecified (SMQ)”. For each of the above SMQs, include all TEAEs which code to a PT included in the Scope=Broad and/or Scope=Narrow.

Note that all AEs meeting the above criteria are to be included. It should not be limited to events that the investigator determined to be related to study drug.

Cases of potential Hy’s Law will be reported separately in a liver function test table.

Hepatic events (including DILI) will also be listed.

